#### Protocol version

Protocol version 4, April 2023

SAP revision history: Version 2

## **1: Introduction**

### *1.1 Background*

Ketone bodies comprise the substances 3-hydroxybutyrate (BHB), acetoacetate, and acetone, which are endogenously produced metabolites present in micromolar concentrations (50-250  $\mu\text{mol/L}$ ) in humans. During stressful conditions such as physical activity, acute illness or in particular prolonged starvation, the production of ketone bodies from the liver (ketogenesis) increase and plasma concentrations may rise manyfold.

Lactate is, just as ketone bodies, an essential endogenously produced metabolite as the end product of glycolysis. All human tissue with glycolytic capacity can produce lactate. During intense exercise, carbohydrate metabolism becomes the primary energy source, which is followed by a marked rise in plasma lactate concentrations.

Lactate and ketone bodies have long been stigmatized as pathogenic markers for fatigue and/or illness. Both are recognized as acidic spill-over agents associated with lactic acidosis and diabetic ketoacidosis, respectively.

The past decade has seen increasing scientific interest into application of ketone body signalling and metabolism to human health. Ketosis is approached endogenously through fasting and time restricted eating regimens or exogenously via ingestion of exogenous ketone body preparations. Targets include maintaining body weight, exercise performance, neurological and heart disease, and immune response to inflammation.

Like BHB, our understanding of lactate is expanding. Continuous lactate turnover has been demonstrated in humans not only in anaerobic but also in aerobic conditions. Lactate is used as an energy substrate in the heart at rest and increases during work. Much alike, the brain takes up lactate during rest, and when lactate availability increases during exercise, the uptake increases correspondingly.

Clinical studies of lactate, and notably exogenous lactate administration not involving exercise, are scarcer when compared to BHB studies. Acute administration in humans has been examined on lipid, protein, and glucose metabolism^3 as well as on appetite and gastric emptying. Research interest in studies of exogenous lactate is rapidly growing in many aspects: on heart failure (NCT06121323), glucose levels and appetite (NCT06265337), traumatic brain injury (NCT06110429), and even depression (NCT06168175).

It is important to distinguish between endogenous ketosis - or lactatemia - and exogenous compounds elevating ketone and lactate concentrations. Endogenous ketosis is a dynamic process with multiple inputs and regulatory points, while exogenous ketones can offer the advantages of elevated ketone levels without raising circulating lipids or necessitating carbohydrate restriction.

Of the ketone bodies, BHB has most scientific interest, as it is the quantitatively dominating ketone body and activate certain signal pathways. BHB comes in two stereoisomeric forms (D-BHB and L-BHB). D-BHB is predominantly produced in the liver, while L-BHB is found in much smaller quantities in the body. Commercially available ketone body preparations include ketone salts, medium-chain triacylglycerides (MCTs), and ketone esters.

Lactate comes in two stereoisomeric forms as well, L-Lactate and D-Lactate. L-Lactate is produced from glycolysis and is the predominant physiological enantiomer within human physiology. Commercially available lactate preparations exist predominantly as lactate salts.

The fact that both compounds have an active isomeric form, and both have potential pleiotropic effects on human health has led to the discovery of a new compound: (3R)-3-Hydroxybutyl (2S)-2-hydroxypropanoate (LaKe).

LaKe is a novel exogenous ketone body-lactate ester preparation for oral use yielding the biologically active isoform of both substances, the D-BHB and S-Lactate while being salt-free (see Figure 2). Ingestion of appropriate doses raise the plasma concentrations of BHB and lactate, effectively mimicking concentrations of BHB seen after days of fasting and lactate concentrations after light physical activity.

### *1.2 Hypothesis*

Being the first clinical trial in humans investigating LaKe, we hypothesize that the beneficial effects of circulating BHB and lactate observed in acute studies can persist with prolonged treatment. Thus, the primary hypothesizes are that a 28-day treatment with LaKe increases insulin sensitivity through the antilipolytic effects of BHB and lactate while enhancing cardiac output during acute-on-chronic intervention. The secondary hypothesizes are that 28-day treatment with LaKe compared with placebo: a) is safe and tolerable, b) decreases lipolysis, c) decreases fat and body weight, d) changes in the level of incretin hormones.

### *1.3 Objectives*

To explore the impact on 28-day modulation of circulating BHB and lactate levels on insulin sensitivity, heart function, safety, lipolysis, body composition and appetite hormones in healthy middle-aged subjects with obesity.

## **2: Study design**

### *2.1 Trial design*

This is a single-center, randomized, double-blind, placebo-controlled crossover study of the effects of 28-day treatment with a novel lactate-ketone ester in healthy middle-aged subjects with obesity.

### *2.2 Randomization*

Participants are randomized 1:1 to receive either oral LaKe (25 mL, Mmimetika Biosciences, Aarhus, Denmark) x 2 daily or non-caloric placebo drink x 2 daily. Each study period lasts 28 days separated by a 28-day washout period.

### *2.3 Endpoints*

**Primary:** The study has two co-primary endpoints:

- 1) Between-treatment difference in cardiac output during acute-on-chronic intervention
- 2) Between-treatment difference in insulin sensitivity during acute-on-chronic intervention

**Secondary:** Between-treatment difference in:

- 1) Safety and tolerability: 10-item Beverage tolerability Questionnaire (BTQ)

- 2) Other echocardiographic parameters: Left ventricular ejection fraction, global longitudinal strain, left ventricular end-diastolic volume, left ventricular end-systolic volume, tricuspid annular plane systolic excursion, mitral inflow velocities (E and A), mitral plane velocities in the lateral mitral annulus (e' and s'), global work index (GWI)
- 3) Lipolysis
- 4) Body composition
- 5) Hormones and metabolites

**Exploratory:** Between-treatment difference in:

- 1) Lactate and BHB concentrations
- 2) Acid-base status
- 3) Biochemic 'safety': concentration measurements of CRP, sodium, potassium, leukocytes, thrombocytes
- 4) Validated questionnaires on appetite and mental well-being

**Timing of endpoints:** The primary and secondary endpoints are measured at each study visit following the 28-day treatment period.

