### **6 Statistical plan**

#### 6.1 Statistical methods

The mean between-treatment ( $\pm 95\%$  CI) change in the primary endpoints of cardiac output (CO) and insulin sensitivity, as well as other single-time-point outcomes, will be analysed using a linear mixed-effects model with fixed effects for treatment and treatment sequence (order) and a random intercept for participant to account for within-participant correlation. Fixed effects will be estimated using a restricted maximum likelihood (REML) procedure and compared using the Kenward–Roger method. Estimated marginal means (EMMs) for treatment will be obtained from the fitted model, and pairwise between-treatment differences will be tested. For log-transformed outcomes, EMMs will be back-transformed to the original scale and reported as geometric means.

Analysis of temporal effects during the acute-on-chronic intervention (repeated-measures data) will be conducted using linear mixed-effects models with fixed effects for treatment, time, and their

interaction, as well as treatment sequence (order), and random intercepts for participant and for visits nested within participants. Fixed effects will be estimated using a restricted maximum likelihood (REML) procedure and compared using the Kenward–Roger method. Estimated marginal means (EMMs) for treatment will be obtained at each time point from the fitted model, and pairwise between-treatment differences will be tested at each time point. For log-transformed outcomes, EMMs will be back-transformed to the original scale.

Assumptions for the statistical analysis will be assessed through inspection of linearity, homoscedasticity, and normality of residuals using plots (residuals vs. fitted values, scale–location plots, and normal Q–Q plots). If violations occur, including significant skewness of residuals or outcome variables, data will be log-transformed and reported accordingly. To enable log transformation, a small constant will be added to all values if multiple observations of 0.0 are present in the dataset. For log-transformed variables, results will be displayed on a logarithmic scale, and between-treatment effects will be expressed as relative changes derived from the model outcomes. If neither the original linear mixed model nor the log-transformed linear mixed model can be applied, data will instead be analysed using McNemar’s exact test, assuming that order and visit have no effect, with a contextual cut-off applied for classification.

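### Acid-base status and the exploratory 'safety' chemistry are summarised as mean between-treatment differences, which with about 10 participants cannot show one participant's abnormal result

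*SAP*

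**What the plan says.** SAP section 2.3 opens the exploratory list with "Exploratory: Between-treatment difference in". Under that heading stand acid-base status and "Biochemic 'safety': concentration measurements of CRP, sodium, potassium, leukocytes, thrombocytes". No reference range or abnormality threshold is attached to either.

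Section 6.1 says that the primary endpoints "as well as other single-time-point outcomes, will be analysed using a linear mixed-effects model". For the output it says: "Estimated marginal means (EMMs) for treatment will be obtained from the fitted model, and pairwise between-treatment differences will be tested". Repeated measures are handled in the same way, time point by time point. Section 5.1 applies a two-sided 5% threshold to every analysis.

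The one method in 6.1 that does not compare means is an exact McNemar test. It is used only if neither the original nor the log-transformed mixed model can be applied, and its cut-off is left to context. The one individual-level item with a bearing on safety is in section 4.2, where the CONSORT diagram is to give reasons for withdrawal. Section 5.2 leaves participants who cannot complete both periods, for reasons named in 4.2, out of the final analysis. Those reasons include safety concerns.

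On setting, section 1.2 begins: "Being the first clinical trial in humans investigating LaKe". Section 3 plans 10 participants.

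**The concern.** The chemistry is labelled as safety, in the first human trial of the compound. For such data a reader wants to know two things: whether the group moved, and whether any individual went out of range. The planned output answers only the first.

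An excursion in one of 10 people moves the mean by a tenth of its size and also inflates the standard error used to test that mean. Followed as written, the analysis could report no significant difference in potassium or acid-base status although one participant was clearly abnormal on LaKe, and nothing in the planned summary would show it.

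The exclusion in 5.2 adds to this. A participant who stopped because of an abnormal result would not contribute even to the mean.

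**Working it through.** **1. The plan's own sample size.** Section 3 gives differences of 30% × 3.0 = 0.9 mg/kg/min (SD 0.9) and 25% × 5.6 = 1.4 L/min (SD 1.4), so difference/SD = 1.0 for both. In a paired t-test (noncentral t, two-sided 5%, 9 df), taking the stated SD as the SD of the within-participant difference, 10 participants give power 0.803. The 10 is reproduced, and it is also the number that carries the safety chemistry.

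**2. One abnormal participant, in formula.** Work in units of the SD of the within-participant difference. Nine participants have no effect and one is shifted by *k*.
- Expected mean difference: *k*/10.
- Expected sample variance of the differences: 1 + *k*²/10.
- At *k* = 5: mean 0.5, variance 3.5, standard error √(3.5/10) = 0.59, ratio about 0.85.
- At *k* = 7.5: mean 0.75, variance 6.625, standard error 0.81, ratio about 0.92.
- The critical value on 9 df is 2.26. As *k* grows, *t* tends to 1 and P to 0.34.

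**3. The same by simulation.** Paired t-test, *n* = 10, at least 300,000 runs per row. The test stands in for the treatment contrast of the mixed model with complete data.

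| *k*, one participant | share with P<0.05 |
|---|---|
| 0 | 5.0% |
| 3 | 3.8% |
| 5 | 1.7% |
| 7.5 | 0.3% |
| 10 | 0.03% |

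The more extreme the single value, the less likely the test is to flag it.

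**4. On measurement scales (all SDs and shifts are assumptions).**
- Potassium, SD of differences 0.3 mmol/L, one participant 1.5 mmol/L higher: *k* = 1.5/0.3 = 5, mean shift 0.15, P<0.05 in about 1.7%.
- Potassium, SD of differences 0.3 to 0.5, one participant 2.0 mmol/L higher: mean shift 0.2, 95% CI half-width about 0.50 to 0.57, P<0.05 in 0.6% to 2.7%.
- pH, SD of differences 0.02, one participant 0.15 lower: *k* = 0.15/0.02 = 7.5, mean shift −0.015, P<0.05 in about 0.3%.

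**5. How far the pattern matters.** With two of 10 shifted, the share is about 8% at *k* = 3, 4.7% at *k* = 5 and 1.4% at *k* = 7.5. With three shifted by 5 SDs it is about 18%. With all 10 shifted by 1 SD it is about 80%, because that is the design case in step 1.

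**6. The McNemar fallback.** If *m* discordant participants all go one way, P = min(1, 2 × 0.5^*m*). One gives P = 1.0, five give 0.0625 and six give 0.031. Even with a defined cut-off, it cannot flag one participant.

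**7. What a count would show.** One case appears as 1/10. If the true on-treatment rate is 5%, 10%, 20% or 30% (assumed range), the chance that at least one of 10 is abnormal, 1 − (1 − rate)^10, is 40%, 65%, 89% or 97%. With 0/10, the exact two-sided 95% upper limit is 1 − 0.025^(1/10) = 31%.

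**The case against.** **The protocol may already cover this.** Adverse-event reporting and review of abnormal laboratory values may be set out there, and nothing in the SAP forbids listings. This stands as a limit. A reader might infer that safety is unmonitored, and one document cannot support that. The choice of summary for these endpoints, however, is the SAP's own.

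**The secondary safety hypothesis does not rest on these items.** A reader might infer that the claim in section 1.2 that LaKe is safe would be judged on the acid-base and chemistry results. The text does not say so. The secondary endpoint named for safety and tolerability in 2.3 is a beverage tolerability questionnaire, and the laboratory items are exploratory. The objection is right, and it is also a reason not to promote them: that would change the endpoint hierarchy and might conflict with the protocol.

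**The mean difference has its own value.** Section 1.1 says that ingestion raises plasma BHB and lactate, so a modest shift in most participants is at least as plausible as one excursion. A common shift of 1 SD is detected about 80% of the time and could leave every value in range. This stands: counts should be added to the mean difference, not put in its place.

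**The background is easily over-read.** Of ketone bodies and lactate, section 1.1 says: "Both are recognized as acidic spill-over agents associated with lactic acidosis and diabetic ketoacidosis, respectively". A reader might take this as saying that the ester risks acidosis. The sentence describes how the two substances have been regarded, and the section goes on to separate endogenous from exogenous elevation. The point here does not need it.

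**Means are not literally the only output.** The McNemar fallback, the residual plots and the withdrawal reasons exist. The first is conditional and cannot flag one person. The second are assumption checks whose prescribed consequence is log transformation. The third covers only those who leave. They qualify the word only, without closing the gap.

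**Applying 6.1 to exploratory endpoints is an inference.** They are not named there, and the timing sentence in 2.3 covers primary and secondary endpoints. The reference to other single-time-point outcomes, with the repeated-measures paragraph, is the natural reading, and no other method is offered.

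**Conclusion.** The point holds as a limit of the planned summary. For acid-base status and the exploratory safety chemistry, the SAP plans model-based mean differences, apart from a conditional fallback with an undefined cut-off. With 10 participants that output cannot show an abnormal result in one of them: P<0.05 in about 1.7% to 0.3% of trials for a single shift of 5 to 7.5 SDs.

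The percentages rest on a paired t-test as stand-in, normal differences, no effect in the other nine participants and assumed shift sizes. They change when several participants are affected, but the inability to identify an individual does not depend on them. The consequence is one of interpretation: a non-significant result for these items is not evidence that no participant was abnormal. No primary result is affected.

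**What to change.** In section 6.1, keep the between-treatment mean difference for acid-base status, CRP, sodium, potassium, leukocytes and thrombocytes, and add beside it, for each treatment:

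- the number of participants with any value outside the laboratory reference range, over the number with data;
- the minimum and maximum;
- a listing, or a paired plot, of each participant's LaKe and placebo values.

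State that this summary covers every participant with data, including those left out of the efficacy analysis under 5.2. The ranges are for the sponsor and the laboratory to name in advance. Leave the items at exploratory level in 2.3. Add a sentence that a non-significant mean difference will not be reported as absence of individual abnormalities.

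The cost is one extra table and one listing from data already collected. The downside is that isolated out-of-range values will appear, under placebo as well, and will need comment.

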#### 2.4 Data integrity

The clinical trial data will be collected and stored in a REDCap database in line with the local patient data integrity administration policy (administered by Aarhus University).

### **3 Cohort size**

Power calculations were conducted independently for each co-primary outcome. The outcomes are analysed and interpreted independently, and the statistical considerations, including power and sample size calculations, are specific to the outcome presented here. Pre-specified co-primary outcomes will be reported regardless of significance in separate analyses and manuscripts without interaction

For the co-primary outcome of insulin sensitivity assessed by a hyperinsulinemic-euglycemic clamp after ingestion of LaKe on the trial day, we aim to detect a relative difference of 30 % (from the mean  $3.0 \text{ mg} \cdot \text{kg}^{-1} \cdot \text{min}^{-1}$  with a standard deviation of  $0.9 \text{ mg} \cdot \text{kg}^{-1} \cdot \text{min}^{-1}$ ), a power of 80 %, and a two-tailed significance level of 5 %. Thus, 10 participants need to be enrolled.

For the co-primary outcome of CO assessed by echocardiographic measurements after ingestion of LaKe on the trial day, we anticipate an increase of CO up to 7.0 liter/min and therefore aim to detect a relative difference of 25 % (from the mean 5.6 liter/min with a standard deviation of 1.4 liter/min), a power of 80 %, and a two-tailed significance level of 5 %. Thus, 10 participants need to be enrolled.

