### **5 Statistical principles**

#### 5.1 Statistical thresholds

Confidence intervals (95%) and P values are two-tailed. A P value of  $<0.05$  is deemed statistically significant for all conducted analyses.

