Secondary endpoints will be analysed and interpreted independently of the primary endpoint results and without adhering to a hierarchical testing sequence. The analysis methods for the secondary endpoints will mirror those outlined for the primary outcomes. No imputation will be performed for missing data.

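### Do two primary endpoints, each tested at 5%, need an adjustment or a disclaimer for error across the pair?

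*SAP*

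**What the plan says.** Section 2.3 of the SAP states: "The study has two co-primary endpoints". They are the between-treatment differences in cardiac output and in insulin sensitivity during the acute-on-chronic intervention. Section 1.2 introduces its primary hypotheses in the plural, then puts both effects in one sentence: treatment "increases insulin sensitivity through the antilipolytic effects of BHB and lactate while enhancing cardiac output during acute-on-chronic intervention".

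Section 3 sets out how the pair is handled. Sample size is worked out separately for each endpoint, each with "a power of 80 %, and a two-tailed significance level of 5" per cent, and each calculation gives 10 participants. The section says "The outcomes are analysed and interpreted independently", and that its statistical considerations apply only to the outcome in question. Both results will be "reported regardless of significance in separate analyses and manuscripts without interaction".

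Section 5.1 applies one threshold throughout: P below 0.05 is "deemed statistically significant for all conducted analyses". Section 6.1 says that the secondary endpoints are read independently of the primary results, "without adhering to a hierarchical testing sequence". The SAP does not split alpha between the primaries, order them or require both to succeed, and it states no error rate for the pair.

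**The concern.** Two tests at 5% give two chances of a false positive, so the chance of at least one false primary finding is above 5% when neither effect is real. The SAP neither controls this nor states it.

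The label adds to the doubt. Co-primary is often understood to mean that both endpoints must succeed, in which case no adjustment is needed, and the single sentence in Section 1.2 can be read that way. Section 3 lets each endpoint stand alone. Because the results go to separate manuscripts, a reader of one paper might see a positive co-primary result without the other result, and might take 5% as the error rate for the whole trial.

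At stake would be how far a single positive primary result can be trusted as a finding of the trial as a whole.

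**Working it through.** **Inputs.** From Sections 3 and 5.1: two endpoints, two-sided 5% each, 80% power, 10 participants. Insulin sensitivity: mean 3.0, SD 0.9, difference 30%. Cardiac output: mean 5.6, SD 1.4, difference 25%. From Section 2.1: crossover design, so the comparison is paired.

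**The plan's own figure.** Standardised effects:

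- insulin sensitivity: 0.30 × 3.0 / 0.9 = 1.0
- cardiac output: 0.25 × 5.6 / 1.4 = 1.0

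A paired t-test with n = 10 has 9 degrees of freedom and noncentrality 1.0 × √10 = 3.16. Its power at two-sided 0.05 is 0.803; n = 9 gives 0.748. So 10 participants is reproduced for each endpoint, provided that the stated SDs are those of the within-participant difference. The SAP does not say whether they are.

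**Error across the pair, neither effect real.** If the endpoints are independent, 1 − (1 − 0.05)² = 1 − 0.9025 = 0.0975. The upper bound for any dependence is 0.05 + 0.05 = 0.10. For correlated endpoints (the correlation is assumed, as the SAP gives none):

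| Correlation | Bivariate normal | Simulated paired t, n = 10 (200,000 runs) |
|---|---|---|
| 0 | 9.75% | 9.7% |
| 0.3 | 9.5% | 9.5% |
| 0.5 | 9.1% | 9.2% |
| 0.8 | 7.8% | 8.0% |
| 0.9 | 7.0% | 7.3% |

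**Error when only one effect is absent.** Only one test can then give a false positive, so the figure is 5%.

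**Error of each endpoint's own claim.** It is 5% in every case, whatever the correlation. This is the error rate that matches what Section 3 says will be concluded.

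**What an adjustment would cost at n = 10.**

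- Equal split, 0.025 each: error across the pair is 1 − 0.975² = 0.0494 if independent, and power per endpoint falls from 0.803 to 0.682. Reaching 80% needs 13 participants (0.835; 12 gives 0.793).
- Holm, both effects real: power per endpoint is 0.764 at correlation 0 and 0.741 at 0.8. Reaching 80% needs 11 or 12 participants, depending on the correlation (11 gives 0.797 at correlation 0.8).
- Holm, one effect real: power is about 0.68–0.69.

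These power figures carry the same assumption about the SDs.

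**If both endpoints had to succeed.** No alpha split would be needed, but with independent endpoints power for both would be 0.8031² = 0.645. Nothing in the SAP sets this rule.

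**The case for a change.** The strongest case for a change grants that each 5% is right and asks only for candour. Section 3 describes how the endpoints are handled but never states the consequence for the pair. Section 6.1 at least says outright that the secondary endpoints follow no hierarchy. A sentence would cost nothing, and the separate manuscripts make it useful.

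Part of this stands. The SAP gives no figure or disclaimer for error across the pair, and co-primary is a loose label for two endpoints that are each read alone.

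The rest is weaker:

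- **Disclosure.** Separate power calculations, separate interpretation, considerations specific to each outcome and one 5% threshold amount to an open statement of per-endpoint inference. Section 6.1 uses much the same language for the secondary endpoints and is equally silent on error rates, so the contrast is thin.
- **The success rule.** That a win on either endpoint makes the trial a success is inferred; the SAP defines no such rule.
- **The joint reading.** Section 1.2 speaks of more than one primary hypothesis, and Section 3 shows how the term co-primary is meant here.
- **Selective reporting.** The plan commits to this: "Pre-specified co-primary outcomes will be reported regardless of significance in separate analyses and manuscripts without interaction". It does not say that either paper will omit the other result, and a paper that calls its endpoint co-primary tells the reader that another exists.

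The SAP also cites a protocol that was not available here, so a multiplicity rationale in that document cannot be excluded.

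**Conclusion.** The arithmetic behind the concern is sound. With neither effect real, the chance of at least one false primary finding is about 8–10% for an assumed correlation between 0 and 0.8. It is 5% if only one effect is absent, and 5% for each endpoint's own claim in every case.

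No change to the plan follows. Cardiac output and insulin sensitivity are different questions, the SAP fixes in advance that each is answered separately, and it commits to reporting both. Whether error should be controlled across two such questions is a matter of judgement, and leaving it uncontrolled is a fair trade-off here. Adjustment would take per-endpoint power at 10 participants from 80.3% to roughly 68–76%, or raise enrolment to 11–13, to support a trial-wide claim that the plan does not make. A sentence stating that no control across the pair is claimed would be harmless and could go into the manuscripts. It would mostly restate Sections 3 and 5.1 and would change no estimate, confidence interval, P value or decision.

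This rests on the claims staying per endpoint, as Section 3 has them. If a single trial-level claim were made on whichever endpoint succeeded, the 8–10% would be the relevant error rate.
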